Design:

This study is a prospective and single blinded randomized control trial. The inclusion or the exclusion criteria will be assessed by the same physician before the patients are invited to join the trial. After the selected patients have signed the informed consent sheets, they will be randomized into two groups (21 patients in each group), the radial shockwave therapy group (RSWT group), the botulinum toxin injection group, and the control group. The randomization will be generated by a computer program and the allocation will be done with concealed envelops. Both the patients and the examining physicians are blind to the allocation. Treatment will be performed by another independent physician.

Participants:

Totally, 42 patients will be recruited from the department of Physical Medicine and Rehabilitation of the Taipei MacKay Memorial Hospital. Eligible subjects should meet the following inclusion criteria: (1) aged between 18 ~ 80 years old; (2) at least 6 months since onset of last stroke; (3) having at least 1+ in modified Ashworth Scale (MAS) score at the spastic elbow; (4) most important of all, read and signed the inform concern of this study.

The exclusion criteria are the following: (1) patients with elbow contracture (MAS=4); (2) patient who had prior history of botulinum toxin, phenol, alcohol injections, intrathecal baclofen pump or rhizotomy in six months; (3) having evidence of cognitive deficit; (4) having local infection, severe inflammation or otherwise lesion that is not suggestive for ESWT; (5) patient with serious medical problems, as uncontrolled hypertension,

coagulopathy, recent severe hemorrhage, neoplasm, severe hepatic disease, epilepsy, cutaneous pathology, mental retardation.

During the study period, physical therapy including range of motion (ROM) exercises, stretching, and others remained unchanged. Also, the doses of medication which might affect spasticity were not changed.

Interventions:

For each group, totally 3 section of therapy will be given in an interval of one week. The shock wave will be given by a two combined ESWT device from which 3000 impulses of shock waves with energy flux density of 1.5 bars and frequency of 5 Hz are delivered in the radial shock wave therapy group. For botulinum toxin group, botulinum toxin (dilution 500 U/2 mL in saline 0.9%) was administered. For the control group, a sham probe will be contacting the skin with the same therapeutic sound made. However, no energy will be delivered from the sham probe. The location of the applied therapy will be at biceps, flexor carpi radialis (FCR) and flexor carpi ulnaris (FCU) muscles.

Outcome measures:

The primary outcome of this study include, elbow and radio carpal joint range of motion (ROM), modified Ashworth scale (MAS), modified Tardieu scale (MTS), and Fugl-meyer assessment (FMA). The evaluation will be done before therapy sections, immediately, 1 month after, and 3 months after 3rd section of therapy. All examination will be done by the same examining physician who is blind to the allocation.

Modified Ashworth scale (MAS). The definition of the measured scales were as that proposed by Bohannon and Smith.³ Briefly, elbow joint range of motion will be performed manually. MAS is graded by the resistance felt during passive range of motion. However, for convenience in the statistical analysis, MAS 1+ was substituted by scale of 2, and 2, 3, and 4 were substituted by 3, 4, and 5, respectively.

Modified Tardieu scale (MTS). The definition of the measurement was as that proposed by Boyd and Graham (modified from Tardieu scale).^{4,5} In brief, the measurement of elbow and radio carpal range of motion will be performed at a slow and a fast velocity. The resulted joint angles at two speeds will be measured by goniometer. R1 angle is defined as angle of catch after a fast speed stretch and R2 angle is defined as angle measured during slow speed range of motion. The average of three testing will be used for analysis. The quality of muscle reaction during measurement will also be scaled.

Fugl-meyer assessment (FMA) The Fugl-Meyer assessment is designed to assess motor recovery following stroke. The maximum score of motor function of upper limbs were 66. It is a relatively simple assessment to administer and requires minimal training. The overall reliability for this instrument was high, as were the reliability measurements for the subsections of this assessment.

Statistical analysis.

All statistic data will be analyzed by SPSS statistical software, version 20.0 (SPSS Inc., Chicago, USA). The homogeneity of patient demographic

characteristics in both comparative groups A and B were calculated with chi-square test for qualitative variables (gender, stroke subtype, affected site) and the ANOVA test for quantitative variables (age, weight, height, body mass index [BMI], time since onset of stroke). The differences between 3 groups were investigated using the repeated measures ANOVA followed by the Bonferroni post hoc tests. Statistical significance was set at $P<0.05$.

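### The plan counts two groups of 21 (42 patients) but names, treats and compares outcomes in three arms, so the stated numbers cannot all hold

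*Combined protocol and SAP*

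**What the plan says.** Four sections of the combined protocol and SAP bear on the number of groups.

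- **Design.** Patients are "randomized into two groups (21 patients in each group". The list that follows in the same sentence has three entries: the radial shockwave group, then "the botulinum toxin injection group, and the control group".
- **Participants.** The total is fixed separately: "Totally, 42 patients will be recruited".
- **Interventions.** Each of the three arms has its own entry. Shock waves "are delivered in the radial shock wave therapy group"; the next entry begins "For botulinum toxin group, botulinum toxin"; and the third reads "For the control group, a sham probe will be contacting the skin".
- **Statistical analysis.** The baseline comparison concerns "characteristics in both comparative groups A and B", labels that appear nowhere else. The outcome analysis is a three-group one: "The differences between 3 groups were investigated", by repeated measures ANOVA with Bonferroni post hoc tests.

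No section gives an allocation ratio, a target difference, an SD, a power or a dropout allowance.

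**The concern.** The group size and the total agree with each other only if there are two arms, while the arm list, the interventions and the outcome analysis all describe three. The documents do not show whether the number of groups, the group size or the total is the mistake.

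Three things depend on the answer. The first is the allocation list: Design says that it is computer-generated and applied through concealed envelopes, and a three-arm list cannot be specified from these counts. The second is the recruitment target, which is either 42 or 63 if there are three arms. The third is the precision of every pairwise comparison, which rests on 21 or on 14 patients per arm. In addition, the baseline comparison is worded for two undefined groups, so it is unclear which patients it covers.

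**Working it through.** **Inputs from the documents**

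| Input | Value | Section |
|---|---|---|
| Groups as counted | 2 | Design |
| Patients per group | 21 | Design |
| Total | 42 | Participants |
| Arms named | 3 | Design |
| Arms given an intervention | 3 | Interventions |
| Groups in baseline comparison | 2 (A and B) | Statistical analysis |
| Groups in outcome comparison | 3 | Statistical analysis |
| Significance level | 0.05, sidedness not stated | Statistical analysis |

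**Step 1: reproduce the stated total.** Total = groups × group size = 2 × 21 = 42. This matches exactly, so 21 and 42 are consistent for two arms.

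**Step 2: three arms, keeping the group size.** 3 × 21 = 63. The shortfall in the stated total is 63 − 42 = 21 patients (21/42 = 50% more than stated).

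**Step 3: three arms, keeping the total.** 42/3 = 14 per arm. That is 21 − 14 = 7 fewer than stated (7/21 = one third).

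**Step 4: effect on precision.** With equal arms and a common SD σ, the standard error of a difference between two arms at one time point is σ√(2/n). The ratio at n = 14 to n = 21 is √(21/14) = √1.5 = 1.22.

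**Step 5: detectable difference, for illustration only.** The plan states no power, sidedness or effect size. Assume a two-sided two-sample t-test at one time point, with 2n − 2 degrees of freedom and noncentrality d√(n/2), where d is the difference in SD units. The value 0.05/3 assumes three pairwise contrasts under Bonferroni.

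| Power (assumed) | Alpha | 21 per arm | 14 per arm |
|---|---|---|---|
| 80% | 0.05 | 0.89 SD | 1.10 SD |
| 80% | 0.05/3 | 1.04 SD | 1.30 SD |
| 90% | 0.05 | 1.03 SD | 1.27 SD |
| 90% | 0.05/3 | 1.18 SD | 1.47 SD |

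A hand check at 80% power and alpha 0.05 uses the normal approximation (1.960 + 0.842) × √(2/n). It gives 0.87 SD at n = 21 and 1.06 SD at n = 14, slightly lower than the t-based values, as expected in small samples. Pooling the error over three arms (3n − 3 degrees of freedom) at 80% power gives 0.88 and 1.09 SD at alpha 0.05, and 1.02 and 1.27 SD at 0.05/3. In every t-based case the detectable difference is 1.24 to 1.25 times larger at 14 than at 21 per arm.

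**The case against.** The strongest reply is that this is a slip of the pen. Three arms are named, each is treated, and outcomes are compared across three, so the intention is clear and only the word for the number of groups is wrong. The first half of that is fair: the documents lean towards three arms, and a two-arm reading is the least supported. But changing that one word does not repair the text. Three groups of 21 make 63, which still contradicts 42, so a second number must also change, and nothing says which.

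Other readings fail too. Unequal allocation is ruled out because the text fixes 21 in each group. Two active arms of 21 plus a control would leave no patients for the control. The sentences are continuous prose with no gap or redaction, so a conversion fault is not a plausible explanation.

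Three narrower objections stand. The baseline reference to groups A and B is secondary evidence: ANOVA is planned for the quantitative baseline variables and accommodates three groups, so the phrase may be leftover wording. The detectable differences rest on assumptions that the plan does not make, and they concern a simpler test than the planned repeated measures ANOVA; the contradiction does not depend on them. The missing sample-size justification is also a separate shortcoming, since the counts could be made to agree without it. It matters here only because it would have shown which number was meant.

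**Conclusion.** The concern holds and must be fixed. Taken together, two groups, 21 per group, a total of 42 and three arms are impossible. The gap is 21 patients in the total (42 against 63) or 7 per arm (21 against 14). This part is pure counting and needs no assumption beyond equal arms, which the text itself states.

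If three arms are intended, the practical uncertainty is a 1.22-fold difference in the standard error of a pairwise comparison at one time point, given a common SD. The detectable differences are illustrative; under the planned repeated measures ANOVA they would also depend on a within-patient correlation that is not given. If two arms were intended, the question of 21 against 14 does not arise, but the third arm would then be unexplained in three sections.

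**What to change.** The sponsor should say which numbers are right and make Design, Participants, Interventions and Statistical analysis agree. If an allocation list already exists, the text should be checked against it. The consistent options are:

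1. **Three arms, total of 42.** State three groups of 14, with a 1:1:1 ratio if equal allocation is intended; generate the list for three arms; and reword the baseline comparison to cover all three groups. Cost: wording and an allocation list, no extra patients, and a group size of 14 where 21 is now stated.
2. **Three arms of 21.** Correct the number of groups to three and the total to 63, with the same change to the baseline wording. Cost: 21 patients beyond the stated 42, which is not cheap unless 63 was the real target all along.
3. **Two arms of 21.** Reconcile the third named arm, its entry under Interventions and the three-group outcome analysis with a two-arm design, and define groups A and B. Cost: a change carried through every section.

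Whichever is chosen, add a short statement of the basis for the group size and, for option 1, of the difference that 14 per arm can detect. That statement goes beyond making the counts agree, but it would let a reader confirm the intended number.

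### Patients are said to be blind without exception, but the only sham described is for shockwave; on the three-arm reading both toxin comparisons are at most assessor-blinded

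*Combined protocol and SAP*

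**What the plan says.** Design labels the study: "This study is a prospective and single blinded randomized control trial". The same section then says "Both the patients and the examining physicians are blind to the allocation", without limiting this to any arm or comparison. It adds that a separate physician gives the treatment. The groups it names are radial shockwave, "the botulinum toxin injection group, and the control group", although it counts only two groups.

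Interventions describes each arm in turn. The shockwave arm receives active impulses from a probe. For the toxin arm, "botulinum toxin (dilution 500 U/2 mL in saline 0.9%) was administered". For the third arm, "For the control group, a sham probe will be contacting the skin with the same therapeutic sound made", with no energy delivered.

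Outcome measures names four primary outcomes: range of motion (ROM), modified Ashworth scale (MAS), modified Tardieu scale (MTS) and Fugl-Meyer assessment (FMA). On timing: "The evaluation will be done before therapy sections, immediately, 1 month after, and 3 months after 3rd section of therapy". On the rater: "All examination will be done by the same examining physician who is blind to the allocation".

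Statistical analysis treats the trial as having three arms: "The differences between 3 groups were investigated using the repeated measures ANOVA followed by the Bonferroni post hoc tests".

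**The concern.** The claim of patient blinding is wider than the procedures that could deliver it. The sham probe imitates shockwave. Nothing described imitates an injection for patients who do not get one, and nothing described gives toxin patients a probe. A toxin patient would therefore know that the treatment was active, while a probe patient could not tell active from sham. Expectations would differ between the arms in every comparison that involves toxin.

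As the text stands, a difference between toxin and control, or between toxin and shockwave, could be presented as patient-blinded without support. FMA matters most here, because a motor score depends on the effort the patient makes; that is general reasoning, not a statement in the plan. ROM, MAS and MTS are recorded by an examiner who is stated to be blind, so their main exposure is indirect. One examiner does every assessment, and a patient who knows the treatment could reveal it. The available text contains no instruction against this.

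The blinding label is a smaller, related problem. A trial in which both patients and examiners are blind is not normally called single-blind, and the label does not say which party it means.

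**Working it through.** The plan gives no figure to reproduce on this point. The check sets the procedures for each arm beside the blinding statement and then counts the comparisons affected.

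**What each arm receives (Interventions)**

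| Arm | Probe on skin | Injection |
|---|---|---|
| Radial shockwave | yes, active | none described |
| Botulinum toxin | none described | yes, toxin |
| Control | yes, sham with matching sound | none described |

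**Can the patient be blind within each pair?**

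- Shockwave versus control: probe against matching sham probe. Patient blinding is feasible.
- Toxin versus control: injection against sham probe. The patient can tell which was received.
- Toxin versus shockwave: injection against active probe. The patient can tell which was received.

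**Count on the three-arm reading (Statistical analysis)**

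- Pairs: 3 × 2 / 2 = 3, of which 2 involve toxin.
- Outcome-by-comparison contrasts with the four named primary outcomes: 4 × 3 = 12, of which 4 × 2 = 8 involve toxin.
- FMA contrasts that involve toxin: 1 × 2 = 2.
- Splitting ROM by joint, or MTS into its components, raises both totals but leaves the fraction at 8/12 = 2/3.

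**Count on the two-arm reading (Design)**

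Design and Participants give two groups of 21 and 42 patients in total. 2 × 21 = 42 agrees with that total; 3 × 21 = 63 does not. With two arms there is one comparison:

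- shockwave versus toxin, or toxin versus sham: 1 of 1 affected;
- shockwave versus sham: 0 of 1 affected.

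Because the arm count is unresolved, no number of affected patients is given.

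**Occasions for disclosure (Outcome measures)**

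The assessments after the third session are immediate, at 1 month and at 3 months, so each patient meets the same examiner 3 times after treatment. If the pre-treatment assessment is meant to be repeated before each of the 3 sessions, the second and third sessions add 2 more, giving 3 + 2 = 5. The plural in the schedule leaves this open, so 3 is the minimum.

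**The case against.** The strongest objection is that the finding depends on a contradiction that has to be settled first. The group count, the group size and the total all agree with a two-arm trial, and if those arms are shockwave and sham, the blinding statement is sound. This stands as a condition. It does not remove the point: Design names a toxin group, Interventions describes its treatment, and the analysis compares three groups. Shockwave versus sham alone is the reading that fits the text least well.

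A double dummy may be used without being described. Interventions says that every group has three sessions but not what the toxin arm receives at each, so that arm is under-described. This also stands. The statement that toxin patients are not blind is an inference from the text, and the remedy must leave room for a description of masking. An equal number of sessions does not, by itself, make an injection resemble a probe.

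The consent pages are not in the public text and might tell patients not to disclose their treatment. That is fair. It weakens only the secondary point about disclosure, not the mismatch over patient blinding.

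Two further objections concern weight. The contrast counts measure reach, not bias, and the ranking of outcomes by exposure is not taken from the plan; it does not say, for instance, whether ROM is active or passive. Both are correct, and active ROM would share some of FMA's direct exposure. It is also true that the plan does not say how results will be described, and that assessor blinding is one form of single blinding. But the explicit sentence covers patients without exception, and a reader will rely on it.

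**Conclusion.** The concern holds. Design claims patient blinding for the whole trial, while the described procedures support it only for shockwave versus sham. On the three-arm reading, 2 of 3 comparisons, or 8 of 12 contrasts over the four named primary outcomes, are at most assessor-blinded; 2 of those 8 are on FMA. On a two-arm reading the result is 1 of 1 if toxin is one of the arms and 0 of 1 if it is not.

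The conclusion rests on two assumptions: that toxin is a randomized arm, and that no undescribed double dummy is used. The direction and size of any bias cannot be derived from the documents. Examiner blinding, with a separate treating physician, still gives some protection, so this should be fixed but does not by itself undermine the trial. The mismatch between the single-blind label and the sentence blinding two parties holds on any reading.

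**What to change.** First confirm which arms are randomized and whether any masking of the injection is used.

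If there is no double dummy, replace the blinding sentence in Design with wording such as: *The examining physician is blind to allocation. Patients are blind only between radial shockwave and sham; patients given botulinum toxin are not blind.* Change the label to match, for example *assessor-blinded, with patients blinded between radial shockwave and sham only*. Report each toxin comparison as assessor-blinded only. Add an instruction, repeated at each assessment, that patients must not tell the examining physician which treatment they received; if the consent material already says this, refer to it in the protocol.

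If a double dummy is in use, describe it for every arm under Interventions. The patient-blinding sentence can then stand, and only the single-blind label needs correcting.

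The cost is protocol wording, one line in the report of each toxin comparison, and one patient instruction. The price is a weaker blinding claim for the toxin comparisons. Treatment, sample size and analysis do not change.

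### Wrist angles are primary but patients are selected on the elbow alone; adjusting for the pre-therapy angle would sharpen a comparison that may be diluted and imprecise

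*Combined protocol and SAP*

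**What the plan says.** Under Participants, the spasticity criterion is "having at least 1+ in modified Ashworth Scale (MAS) score at the spastic elbow". The only contracture exclusion is "patients with elbow contracture (MAS=4"). No criterion mentions wrist tone, wrist contracture or wrist range.

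Under Interventions, treatment is not conditional on wrist status: "The location of the applied therapy will be at biceps, flexor carpi radialis (FCR) and flexor carpi ulnaris (FCU) muscles".

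Under Outcome measures, the primary outcomes are "elbow and radio carpal joint range of motion (ROM), modified Ashworth scale (MAS), modified Tardieu scale (MTS), and Fugl-meyer assessment (FMA"). The Tardieu paragraph covers both joints: "the measurement of elbow and radio carpal range of motion will be performed at a slow and a fast velocity". It defines R1 as the catch angle at fast speed and R2 as the slow-speed angle, adds "The average of three testing will be used for analysis", and says that the quality of the muscle reaction is graded. The Ashworth paragraph describes the elbow only, though the primary list could be read as covering the wrist too. The timing is: "The evaluation will be done before therapy sections, immediately, 1 month after, and 3 months after 3rd section of therapy". That is one pre-therapy and three post-therapy assessments.

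Statistical analysis names a repeated measures ANOVA across three groups with Bonferroni post hoc tests, at P<0.05. It names no covariate and no analysis set.

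Design says "they will be randomized into two groups (21 patients in each group") and then lists three groups.

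**The concern.** A patient with a spastic elbow and a wrist that shows no catch, or that hardly moves even at slow speed, meets the criteria and contributes to the primary wrist result. Two things could follow.

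- **Dilution.** If a share f of wrists cannot change much, the average wrist effect shrinks by about that share.
- **Imprecision.** A mix of normal, spastic and stiff wrists would spread the pre-therapy angles widely. That spread carries into the post-therapy angles unless the analysis removes it.

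The plan already collects the pre-therapy angle. If that angle is only the first of four time levels, a comparison of group means does not use it to remove differences between patients. What is at stake is the precision of the wrist comparisons and how a null wrist result can be read.

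**Working it through.** **Starting point.** The plan gives no power, effect size or SD, so there is no power figure to reproduce. Only the group arithmetic can be checked: 2 × 21 = 42 agrees with the stated total, while three named groups give 42/3 = 14 each (three groups of 21 would need 63). Both 14 and 21 per arm are used below.

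**Assumptions, none from the documents.** The effect is 1 SD at a post-therapy visit. The correlation ρ between pre- and post-therapy values is 0.6. Tests are two-sided at 0.05. The share f runs from 0 to 40%.

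**Step 1: dilution.** The all-patient effect is (1−f) times the effect in responsive wrists. Suppose power would be 80% at f = 0. Power is then Φ(2.80 × (1−f) − 1.96), at either sample size.

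- f = 20%: Φ(2.24 − 1.96) = 61%.
- f = 40%: Φ(1.68 − 1.96) = 39%.

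The 80% is only an illustrative start, not a plan figure.

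**Step 2: one-visit pairwise comparison at f = 0.** The standard error of the group difference, in SD units, is √(2v/n). The factor v depends on the analysis:

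- unadjusted post-therapy value: v = 1
- change score: v = 2(1−ρ) = 0.80
- covariate: v = 1−ρ² = 0.64

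Power from the noncentral t distribution:

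| Analysis | SE, n = 14 | 1/SE | Power, n = 14 | Power, n = 21 |
|---|---|---|---|---|
| Unadjusted | 0.378 | 2.65 | 72.1% | 88.5% |
| Change score | 0.338 | 2.96 | 81.3% | 94.2% |
| Covariate | 0.302 | 3.31 | 88.8% | 97.7% |

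Simulation, which allows for chance imbalance in the pre-therapy value, gives about 72%, 82% and 88% at 14 per arm. At the Bonferroni level for three pairs (0.05/3) the formula gives 54.2%, 65.5% and 76.5%.

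**Step 3: against the tests in the planned ANOVA (three arms, four visits, both active arms 1 SD better at every post-therapy visit, 14 per arm).**

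- Group main effect: the pre-therapy visit, where no effect can exist, is averaged in, so the effect becomes (0+1+1+1)/4 = 0.75 SD. The variance factor is (1+3ρ)/4 = 0.70. Power is about 65–66%.
- Group-by-time test: this works within patients, so it already uses the pre-therapy value. Power is about 87%, close to the covariate figure at one visit.

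**Step 4: sensitivity of the gain over change scores (14 per arm).**

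- ρ = 0.4, f = 0 to 20%: gain of 11–14 points.
- ρ = 0.8, f = 0 to 20%: gain of 0–2 points.
- Unresponsive wrists starting 2 SD away, opposite to the treatment effect, with SD 0.5: 64% against 65% at f = 20%, and 44% against 45% at f = 40%. The gain is nil.
- Starting 2 SD away in the other direction: gain of about 9–10 points.

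**Step 5: why by visit.** If the effect faded from 1 to 0.5 to 0 SD over the three visits (f = 0, 14 per arm), a covariate analysis averaged over visits would have about 55% power, against 85% for group-by-time. Averaging over visits is therefore not a safe substitute.

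**The case against.** The case against is strong in several places.

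- **The harm is hypothetical.** Nothing in the documents shows that any enrolled wrist is non-spastic or fixed, and f may be zero. Selecting on the elbow and also measuring the wrist is a legitimate choice of population. This stands, and it is why the point is minor.
- **A covariate does not cure dilution, and the argument is the same for the elbow.** Both stand. The fix is justified by precision alone and should cover the elbow angles too.
- **The planned ANOVA is not weak throughout.** Its group-by-time test nearly matches a one-visit covariate test. This stands. But that test does not say which groups differ or when. Pairwise comparisons do, and there the covariate helps.

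A reader might go further and infer that the wrist comparison is biased or invalid. It is not: randomisation protects it, and dilution pulls the effect towards zero. A reader might also call some wrists untreatable. The documents treat these muscles in everyone, and the most that can be said is that some wrists may have little room to change. Nor does the text show that pre-therapy wrist status will go unreported. Those values are scheduled, and the comparability list in Statistical analysis concerns demographic characteristics, so its silence proves nothing.

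**Conclusion.** The mismatch is real: selection is at the elbow, while treatment and primary angles also cover the wrist. The all-patient wrist comparison remains unbiased and is the right main analysis for the patients enrolled. It may be diluted by an unknown share of wrists, and its group comparisons may be less precise than the collected data allow.

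Under a 1 SD effect, correlation 0.6 and 14 per arm, adjusting for the pre-therapy value raises one-visit pairwise power to about 88%, from 72% unadjusted or 82% with change scores. These figures rest wholly on assumptions. The gain over change scores can be nil if unresponsive wrists start from very different angles, and the gain over group-by-time is small at a single visit.

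It is tempting to conclude that the efficacy result should rest on a subset of responsive wrists. The documents do not support that: they give no cut-offs and no basis for judging how well such a rule would classify wrists, and the subset would be small. The point is an inexpensive improvement that the sponsor could make, not a required correction.

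**What to change.** In Statistical analysis, before unblinding, add wording such as: *Wrist and elbow range of motion and Tardieu R1 and R2 at the three post-therapy visits will be analysed in a model with group, visit and group-by-visit terms, the pre-therapy value of the same measure as covariate, and allowance for correlation within patients. All randomised patients with data will be included. Group differences will be given at each visit with 95% confidence intervals and Bonferroni-adjusted pairwise tests.* State whether the adjustment covers the three pairs within a visit or all nine pair-by-visit comparisons, because the power depends on it.

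Optional and of lower priority: report pre-therapy wrist R1, R2 and muscle-reaction quality by arm, with the number of wrists showing no catch or no slow-speed movement. A null wrist result could then be read in light of how many wrists had room to change.

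The cost is a few sentences and one more term per model, with no new patients, visits or measurements. Eligibility and treatment are untouched. The statements of two groups and of three need reconciling in any case, since they decide whether there are 14 or 21 patients per arm.

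### The six-month exclusion of earlier spasticity treatments omits shock wave therapy, so recently treated patients can enter and their exposure is never recorded

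*Combined protocol and SAP*

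**What the plan says.** All references are to the combined protocol and SAP.

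- **Design** names the arms as "the radial shockwave therapy group (RSWT group), the botulinum toxin injection group, and the control group", and states: "Both the patients and the examining physicians are blind to the allocation".
- **Participants, exclusion criterion 2** removes a "patient who had prior history of botulinum toxin, phenol, alcohol injections, intrathecal baclofen pump or rhizotomy in six months". Shock wave therapy is not on this list.
- **Participants, exclusion criterion 4** is the only eligibility criterion that mentions shock wave therapy. It removes patients "having local infection, severe inflammation or otherwise lesion that is not suggestive for ESWT", which concerns the present state of the limb and not past treatment.
- **Interventions** describes the active shock wave session ("3000 impulses of shock waves with energy flux density of 1.5 bars and frequency of 5 Hz are delivered") and the control session ("a sham probe will be contacting the skin with the same therapeutic sound made"), adding that "no energy will be delivered from the sham probe".
- **Outcome measures** places the last assessment "3 months after 3rd section of therapy", after assessments before treatment, immediately after it and at 1 month.
- **Statistical analysis** lists the baseline characteristics to be compared: gender, stroke subtype, affected site, age, weight, height, BMI and time since stroke. Earlier treatment is not among them, and no covariate or stratification factor is named.

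**The concern.** Criterion 2 appears intended to keep out patients whose limb is still under the influence of a recent spasticity procedure. It does this for one of the trial's two active treatments and leaves out the other. Two things could follow.

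**Carry-over.** A patient given shock waves shortly before entry may have baseline spasticity, range of motion and motor scores that already reflect treatment. Such a patient may have less left to gain. That would shrink the observable shock wave effect, and in a small trial these patients could also fall unevenly between arms by chance.

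**Recognition of the sham.** The sham reproduces contact and sound but not the impulses. A patient who has felt the real device has a basis for noticing the difference. Any influence on outcomes would come through the patient's expectation or effort.

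If exposure is not recorded, neither possibility can be examined at analysis.

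**Working it through.** **1. Does any other part of the plan close the gap?**

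| Provision | Section | Does it deal with earlier shock wave therapy? |
|---|---|---|
| Exclusion 2, six-month list | Participants | No; not listed |
| Exclusion 4, local lesions | Participants | No; suitability only |
| Inclusion 3, elbow MAS of at least 1+ | Participants | No; a treated patient with residual spasticity still qualifies |
| Inclusion 2, at least 6 months since stroke | Participants | No; leaves time for earlier treatment |
| Stable physical therapy and medication | Participants | No; covers the study period only |
| Baseline comparison | Statistical analysis | No; earlier treatment not included |

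The gap stands.

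**2. Is carry-over possible on the plan's own terms?** The 3-month assessment shows that the investigators consider an effect at that time worth looking for. It does not show that the effect lasts that long. Carry-over is therefore possible but not established.

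**3. Illustration of dilution.** The plan gives no sample-size calculation, so there is no stated figure to reproduce.

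*From the document:* 42 patients. The Design section describes two groups of 21 but names three arms, so both arm sizes are shown: 21, and 42/3 = 14.

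*Assumed, found nowhere in the document:*
- share exposed, r, from 0 to 30%;
- exposed patients have half the room to improve;
- undiluted effect of 1.2 SD;
- two-sided alpha of 0.05/3 = 0.0167 per pairwise comparison (Bonferroni over three pairs; the plan names Bonferroni tests but not this figure);
- a two-sample t-test as a stand-in for the planned repeated-measures analysis.

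*Formulas:* diluted effect d = 1.2 × (1 − r/2); sample-size inflation = 1/(1 − r/2)²; power from the noncentral t distribution with 2n − 2 degrees of freedom and noncentrality d√(n/2).

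*Example, r = 0.30:* d = 1.2 × 0.85 = 1.02; inflation = 1/0.7225 = 1.38; noncentrality = 1.02 × √7 = 2.70 at 14 per arm.

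| Share exposed r | d | Inflation | Power, 14 per arm | Power, 21 per arm |
|---|---|---|---|---|
| 0% | 1.20 | 1.00 | 0.727 | 0.912 |
| 2% | 1.188 | 1.02 | 0.717 | 0.906 |
| 5% | 1.17 | 1.05 | 0.702 | 0.896 |
| 10% | 1.14 | 1.11 | 0.675 | 0.878 |
| 20% | 1.08 | 1.23 | 0.620 | 0.836 |
| 30% | 1.02 | 1.38 | 0.562 | 0.786 |

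The documents cannot say which row applies.

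**4. Which outcomes could sham recognition reach?** MAS is resistance felt by the examiner during passive movement. The MTS angles are read by goniometer after stretches at two speeds. The examiner is stated to be blind, so the clearest route for patient expectation is the Fugl-Meyer assessment, which depends on the patient's effort. No figure can be put on this.

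**The case against.** **The omission may have no practical effect.** Earlier shock wave treatment could be rare among the candidates, and the documents do not say. This stands: the illustration has to start at 0%, where nothing is lost, and at 2–5% the loss is slight.

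**Randomisation balances earlier exposure.** This also stands, on average. A reader might infer that admitting treated patients biases the comparison. The documents do not support that: exposure precedes allocation, so the risk is dilution, noise and chance imbalance. Randomisation does not remove dilution, and does not guarantee balance with 42 patients.

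**The assessment schedule does not prove a 3-month effect.** Correct. A reader might infer that the plan itself assumes the effect persists, but an assessment at 3 months could equally be there to see it fade.

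**The six-month exclusion does not secure blinding.** This stands in large part. Recognition depends on ever having felt the device, so someone treated seven months before entry could still tell. The sham's missing energy is also a feature for every control patient, and earlier exposure only adds to it. A reader might infer that the exclusion would protect the blind, or that all outcomes are open to patient expectation. Neither follows.

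**Every listed item is an injection, implant or operation, and the window may not suit shock wave therapy.** The plan does not justify the window for any treatment. Reusing it is a matter of consistency, not evidence. That does not explain leaving out a treatment under test, and it does not excuse failing to record exposure.

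**Conclusion.** The concern holds as a minor eligibility gap. Criterion 2 screens for recent exposure to one active treatment and not the other, and nothing elsewhere screens for, records or adjusts for earlier shock wave therapy. A partly treated baseline is possible. The likely harm is some loss of sensitivity to the shock wave effect, or chance imbalance, rather than systematic bias. Sham recognition is a secondary risk, bearing mainly on the Fugl-Meyer assessment.

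The size is unknown. The illustrated loss runs from nothing to about 17 percentage points of power at 14 per arm (0.727 − 0.562 = 0.165) and about 13 at 21 per arm (0.912 − 0.786 = 0.126). Those figures rest entirely on the assumed share, room to improve and effect size, and are not estimates for this trial. The omission itself is certain from the text; confidence that it matters in practice is moderate at most. The change is desirable rather than essential.

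**What to change.** 1. In exclusion criterion 2, add extracorporeal shock wave therapy to the affected upper limb, under the window already stated there.
2. At screening, ask about and record any lifetime shock wave exposure, with its date and site.
3. Specify a sensitivity analysis that omits patients with any earlier exposure. Because exposure is fixed before randomisation, the remaining patients can still be compared by allocated arm, with some loss of precision.

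The first change addresses carry-over and only partly reduces sham recognition. The second and third let the effect of older exposure be examined, but do not prevent it.

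The cost is one phrase, one screening question and one sentence in the Statistical analysis section. The downside is that a few candidates at this single centre would be ineligible or would have to wait.
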